10.4. Study cohorts/ data sets to be analysed

A total of 7 cohorts are defined for the purpose of analysis.

10.4.1. Persistence cohorts

10.4.1.1. Total cohort at Month X

The Total cohort at Month X will include all vaccinated subjects in the vaccination stage of study MenACWY-TT-027 (108658) who return for the Month X follow-up. For the analysis of persistence, this will include all vaccinated subjects for whom data concerning persistence endpoint measures are available.

10.4.1.2. According-To-Protocol (ATP) cohort for persistence – MenC at Month X

Analysis of persistence of MenC antibody titres for Month X will be done on ATP cohort for persistence – MenC at Month X. The ATP cohort for antibody persistence – MenC at Month X will include all evaluable subjects:

- who were eligible in study MenACWY-TT-027 (108658).
- who have received the primary vaccination with MenACWY-TT or *Meningitec* or *Mencevax ACWY* during study MenACWY-TT-027 (108658) according to their treatment group.
- who have available assay results for MenC antigen at Month X.
- who have not received a meningococcal vaccine not planned in protocol MenACWY-TT-027 (108658) before Month X.
- who do not have a history of meningococcal disease prior to Month X.
- who comply with the blood sampling intervals defined in Table 5 for Month X.
- who do not have an immunocompromising medical condition.
- who have not received any immunosuppressant(s) or other immune-modifying drug(s), immunoglobulins, any blood products, investigational drugs, and/or investigational vaccines within 30 days of persistence blood sample.
- who were not excluded from the ATP cohort in the primary study MenACWY-TT-027
 (108658) and from the previous ATP persistence cohorts, unless the reason for exclusion
 was either non-compliance with the protocol-defined serum sampling windows or a lack of
 availability of immunogenicity results at previous time point

10.4.1.3. According-To-Protocol (ATP) cohort for persistence – MenAWY at Month X

Analysis of persistence of MenA, W-135 and Y antibody titres at Month X will be done on the ATP cohort for persistence – MenAWY at Month X. The ATP cohort for persistence Month X – MenAWY will include all evaluable subjects:

• who were eligible in study MenACWY-TT-027 (108658).

- who have received the primary vaccination with MenACWY-TT or *Meningitec* or *Mencevax ACWY* during study MenACWY-TT-027 (108658) according to their treatment group.
- who have available assay results for at least one of three antigens (MenA or W-135 or MenY) at Month X.
- who have not received a meningococcal vaccine not planned in protocol MenACWY-TT-027 (108658) before Month X with the exception of a monovalent MenC conjugate vaccine because of suboptimal response to *N. meningitidis* serogroup C after vaccination in the primary study MenACWY-TT-027 (108568).
- who do not have a history of meningococcal disease prior to Month X.
- who comply with the blood sampling intervals defined in Table 5 for Month X.
- who do not have an immunocompromising medical condition.
- who have not received any immunosuppressant(s) or other immune-modifying drug(s), immunoglobulins, any blood products, investigational drugs, and/or investigational vaccines within 30 days of persistence blood sample.
- who were not excluded from the ATP cohort in the primary study MenACWY-TT-027 (108658) and from the previous ATP persistence cohorts, unless the reason for exclusion was either non-compliance with the protocol-defined serum sampling windows or a lack of availability of immunogenicity results at previous time point or re-vaccination with a monovalent meningococcal polysaccharide conjugate vaccine of serogroup C due to suboptimal response to *N. meningitidis* serogroup C after vaccination in the primary study MenACWY-TT-027 (108658).

10.4.2. Booster cohort

10.4.2.1. Booster Total Vaccinated Cohort

The Booster Total Vaccinated Cohort for safety following the booster vaccination will include all vaccinated subjects in the primary vaccination study MenACWY-TT-027 (108658) with a booster vaccine administration documented.

For the analysis of immunogenicity post-booster vaccination the Booster Total Vaccinated Cohort will include all subjects for whom data concerning post-booster immunogenicity endpoint measures are available.

10.4.2.2. Booster According-To-Protocol (ATP) cohort for safety

The Booster ATP cohort for safety following booster vaccination will include all subjects:

- who met all inclusion criteria and no exclusion criteria for the study
- who have received a dose of study vaccine MenACWY-TT or *Meningitec* or *Mencevax ACWY* in the primary study MenACWY-TT-027 according to their treatment group.

- who have not received a vaccine not specified or forbidden in the protocol (subjects who received a vaccine not foreseen by the study protocol from 30 days before until 30 days after administration of the study vaccine dose will be eliminated from the ATP cohort for safety if the vaccine not foreseen by the protocol was administered before the post-vaccination blood sample).
- who have received a booster dose of study vaccine MenACWY-TT in the booster epoch.
- for whom the administration site of the vaccine is known.
- who were not excluded from the ATP cohort for persistence Year 10, unless the reason for exclusion was either non-compliance with the protocol-defined serum sampling windows or a lack of availability of immunogenicity results at Year 10 (pre Booster vaccination).

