10.4.2.4. Booster According To Protocol (ATP) cohort for immunogenicity – MenAWY

At post booster time point, the analysis of immunogenicity for MenA, W-135 and Y antibody titres will be done on Booster ATP cohort for immunogenicity – MenAWY. The Booster ATP cohort for immunogenicity – MenAWY cohort will include all evaluable subjects (i.e. those meeting all eligibility criteria, complying with the procedures defined in the protocol and with no elimination criteria during the study) from the Booster ATP cohort for safety for whom assay results are available for antibodies against at least one of the three antigens (MenA or MenW-135 or MenY) for the blood sample taken one month post-vaccination, and who were not administered a vaccine not foreseen by the study protocol from 30 days before the booster administration until the post-vaccination blood sample and who have not received a MenACWY conjugate vaccine because of sub-optimal response between the vaccination in the primary study MenACWY-TT-027 (108568) and the booster vaccine in this study. If a subject previously received monovalent MenC conjugate vaccine because of suboptimal response to *N. meningitidis* serogroup C after vaccination in the primary study MenACWY-TT-027 (108568), the subject

can still be included in the Booster ATP cohort for MenAWY. The interval between Visit 5 and Visit 6 for inclusion in the Booster ATP cohort for immunogenicity – MenAWY will be defined as 21 to 48 days.

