			MenC titer available post booster No unforeseen vaccinations from 30 days before booster until the postvaccination bleed No MenC or MenACWY conjugate vaccine between MenACWY-TT-027 vaccination and booster due to suboptimal MenC response	MenA, W-135, or Y titer available No unforeseen vaccinations from 30 days before booster until the postvaccination bleed No MenACWY conjugate vaccine between MenACWY-TT-027 vaccination and booster due to suboptimal response
			Interval for inclusion is 21-48 days from vaccination to post bleed	Receiving monovalent MenC conjugate due to suboptimal response is not exclusionary Interval for inclusion is 21-48 days from vaccination to post bleed
			Medications/products/v accines and/or no intercurrent medical conditions that may lead to the exclusion of a subject according to Protocol sections 6.5.2 and 6.6	Medications/products/v accines and/or no intercurrent medical conditions that may lead to the exclusion of a subject according to Protocol sections 6.5.2 and 6.6

Persistence cohorts are described in more detail in Section 6.2.1, Section 6.2.2, Section 6.2.3, and Section 6.2.4.

MenACWY-TT-100 (C0921004)

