6.2.2. Booster ATP Cohort for Safety

The booster ATP cohort for safety will include all subjects:

- who met all inclusion criteria and no exclusion criteria for the study.
- who received a dose of study vaccine MenACWY-TT, Meningitec, or Mencevax ACWY in the primary study (MenACWY-TT-027) according to their vaccine group.
- who did not receive a vaccine not specified or forbidden in the protocol (subjects who
 received a vaccine not foreseen by the study protocol from 30 days before until
 30 days after the study vaccine dose will be eliminated from the ATP cohort for
 safety if the vaccine not foreseen by the protocol was administered before the
 postvaccination blood sample).
- who received a booster dose of study vaccine MenACWY-TT in the booster epoch.
- for whom the administration site of the vaccine is known.
- who were not excluded from either ATP cohort for persistence at Month 126 (ie, MenC or MenAWY), unless the reason for exclusion was either non-compliance with the protocol-defined serum sampling windows or a lack of availability of immunogenicity results at Month 126 (Year 10, prebooster vaccination).

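### Entry to the booster ATP cohorts does not excuse MenC revaccination, so whether revaccinated subjects reach the booster MenA, W-135 and Y analysis depends on which line is programmed

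*Protocol*

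**What the plan says.** **Entry condition.** Protocol 10.4.2.2 takes subjects "who were not excluded from the ATP cohort for persistence Year 10, unless the reason for exclusion was either non-compliance" with the serum sampling windows or absence of Year 10 results. No third reason is listed, and the Year 10 cohort is referred to in the singular. SAP 6.2.2 rewords this to subjects "who were not excluded from either ATP cohort for persistence at Month 126 (ie, MenC or MenAWY), unless the reason for exclusion" was one of the same two. The Year 10 rows of SAP Table 3 repeat the two reasons and name no cohort.

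**What it controls.** Protocol 10.4.2.4 builds the booster MenAWY cohort from evaluable subjects "from the Booster ATP cohort for safety for whom assay results are available for antibodies against at least one of the three antigens". Protocol 10.4.2.3 and SAP 6.2.3 and 6.2.4 also require membership of the booster ATP safety cohort.

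**The two Year 10 persistence cohorts in the Protocol.** The MenC cohort (10.4.1.2) takes only subjects "who have not received a meningococcal vaccine not planned in protocol MenACWY-TT-027 (108658) before Month X", with no exception. The MenAWY cohort (10.4.1.3) has the same rule "with the exception of a monovalent MenC conjugate vaccine because of suboptimal response", and its carry-forward rule lists MenC revaccination as a third excused reason for an earlier exclusion.

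**What is allowed for revaccinated subjects.** Protocol 4.3 admits them to the study so that MenA, W-135 and Y persistence can be followed. Protocol 10.4.2.4 says such a subject "can still be included in the Booster ATP cohort for MenAWY". SAP 6.2.4 agrees, and the MenAWY column of SAP Table 3 states: "Receiving monovalent MenC conjugate due to suboptimal response is not exclusionary".

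**The SAP's own change.** SAP 6.1.2 gives both persistence cohorts the same requirements apart from the titer needed, and its vaccine bullet excepts subjects given MenC vaccine as suboptimal responders. SAP section 10 records their inclusion for all antigens as a change from plan. SAP 8.1 sets their later MenC persistence results, Month 126 included, to half the cutoff.

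**The concern.** A criterion that belongs to MenC may decide who enters the booster analysis of the other three serogroups. A subject excluded from the Year 10 MenC persistence cohort only because of MenC revaccination has neither of the two excused reasons. If the entry condition is read as covering that cohort, the subject fails it and cannot be in any booster ATP cohort, whatever 10.4.2.4 permits.

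Two features suggest that this was not intended. The MenAWY persistence cohort carries the missing excuse explicitly. And Protocol 10.4.2.3 removes revaccinated subjects from booster MenC in a clause of its own, which would be unnecessary if they had already been kept out of the safety cohort.

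At stake is a determinate population for the Month 126 and Month 127 MenA, W-135 and Y booster tables, and for the supportive ATP safety cohort. The subjects in question were selected on a weak MenC response, so their loss would not be random.

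**Working it through.** **Step 1. Trace one subject.** Take a boosted subject, revaccinated with monovalent MenC vaccine and otherwise compliant. Apply each version of the Month 126 persistence rules, then each reading of the cohort named in the entry condition.

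| Persistence rules applied | MenAWY cohort only | MenC cohort | Excluded from neither | In at least one |
|---|---|---|---|---|
| Protocol 10.4.1.2 and 10.4.1.3 | kept | removed | removed | kept |
| SAP Table 1 | kept | removed | removed | kept |
| SAP 6.1.2 vaccine bullet with SAP section 10 | kept | kept | kept | kept |
| SAP 6.1.2 last bullet, read literally | removed | removed | removed | removed |

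Rows 1 and 2 agree because the revaccination exception appears only on the MenAWY side in each. The last row assumes that the subject was excluded from an earlier ATP persistence cohort for revaccination. That bullet is stated to apply to both cohorts and excuses only missed windows and missing results, so the earlier exclusion carries into both. Protocol 10.4.1.3 has an excuse for exactly that situation; SAP 6.1.2 does not.

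The natural reading of SAP 6.2.2 is the third column, excluded from neither. The Protocol wording alone does not choose a column.

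**Step 2. Numbers at risk.** Planned Year 10 numbers are 122 in each ACWY group and 41 in each control group (Protocol 10.3). The number revaccinated is not given; assume 2% to 10%.
- 0.02 × 122 = 2.4 and 0.10 × 122 = 12.2, so about 2 to 12.
- 0.02 × 41 = 0.8 and 0.10 × 41 = 4.1, so about 1 to 4.

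**Step 3. Would the complementary analysis catch it?** It runs when more than 10% of a group's subjects with results are excluded.
- 12/122 = 9.8% and 13/122 = 10.7%, so 13 are needed.
- 4/41 = 9.8% and 5/41 = 12.2%, so 5 are needed.

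Within the assumed range, revaccinated subjects alone do not trigger it. They do count toward it alongside other exclusions.

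**Step 4. Precision.** Protocol Table 17 at 90% for Year 10 is reproduced by exact intervals: 110/122 gives 83.4 to 94.8 (width 11.4 points) and 37/41 gives 76.9 to 97.3 (width 20.4). With 10% removed, 99/110 gives 82.8 to 94.9 (12.1) and 33/37 gives 74.6 to 97.0 (22.4). The loss is small.

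**Step 5. Illustration of a shift.** Suppose that 35% of other subjects and 10% of revaccinated subjects have pre-booster rSBA-MenW-135 at or above 1:8, and that a fraction r is revaccinated. The 35% is close to the 34.7% quoted in Protocol 1.2 at five years for those vaccinated between ages 1 and 2; the 10% is purely assumed. Dropping the revaccinated changes the percentage by 35 − [(1 − r) × 35 + r × 10] = 25r points: 0.5 at r = 0.02 and 2.5 at r = 0.10. The post-booster effect is probably smaller.

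**The case against.** The best reply is that the SAP, as the later document, has already settled the matter. SAP 6.1.2 makes the two persistence cohorts alike, its vaccine bullet keeps revaccinated subjects in both, and section 10 declares this deliberate. The half-cutoff rule in SAP 8.1, which expressly covers Month 126, has an evident use only if these subjects are in the Month 126 MenC persistence analysis. Table 1 is a summary that defers to the detailed sections. In the Protocol, the unnamed cohort can be read as MenAWY, from which these subjects were never excluded. On all of those lines nobody is removed.

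That much stands, and it defeats a stronger inference a reader might draw: that the entry condition definitely removes revaccinated subjects. It does not stand as a full answer. The MenC column of Table 1 contradicts section 10. The last bullet of SAP 6.1.2 sits in the same detailed section as the vaccine bullet and leads the other way. The permission in SAP 6.2.4 stands beside its own requirement of safety-cohort membership and does not override it.

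A second tempting inference, that dropping these subjects flatters the MenA, W-135 and Y results, is also unsupported. No document shows that weak MenC responders respond less to the other serogroups. In the MenCCRM group the first vaccine had no A, W-135 or Y component, so a weak response to it says nothing about them. The overestimation that SAP section 10 mentions concerns MenC persistence only.

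**Conclusion.** The concern holds as an unresolved conflict between cohort rules. The entry condition omits MenC revaccination as an excused reason, and in the Protocol it does not identify its persistence cohort. Depending on the line programmed, revaccinated subjects are either all kept or all lost from the booster MenAWY cohort and the supportive safety cohort.

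Neither the number affected nor any bias can be established from the documents. The counts rest on an assumed 2% to 10% revaccinated, and the 0.5 to 2.5 point shift on assumed positivity as well; neither is an estimate. The consequence is bounded. The affected booster analyses are secondary and descriptive. Primary Month 126 persistence uses the persistence cohorts and does not pass through this condition. The main booster safety analysis uses the Booster Total Vaccinated Cohort and is unaffected. The 10% rule is only a partial safeguard. The correction should be made because it is cheap and makes the population determinate.

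**What to change.** 1. In Protocol 10.4.2.2, SAP 6.2.2 and the Year 10 rows of SAP Table 3, add a third excused reason: revaccination with a monovalent MenC conjugate for suboptimal MenC response.
2. Add the same excuse to the last bullet of SAP 6.1.2.
3. Align the MenC column of SAP Table 1 with SAP 6.1.2 and section 10, in both the unplanned-vaccine row and the earlier-exclusion row.
4. Keep the separate removal of these subjects from booster MenC in Protocol 10.4.2.3 and SAP 6.2.3.

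Pointing the entry condition at the MenAWY Month 126 cohort alone is not an equivalent alternative unless item 2 is also done, because the last bullet of SAP 6.1.2 could still carry an earlier exclusion into that cohort.

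The cost is a few clauses and a matching check of the cohort programming. No new data are needed.

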10.4.2.3. Booster According To Protocol (ATP) cohort for immunogenicity - MenC

At post booster time point, the analysis of immunogenicity for MenC antibody titres will be done on Booster ATP cohort for immunogenicity – MenC cohort. The Booster ATP cohort for immunogenicity – MenC will include all evaluable subjects (i.e. those meeting all eligibility criteria, complying with the procedures defined in the protocol and with no elimination criteria during the study) from the Booster ATP cohort for safety for whom assay results are available for antibodies against MenC antigen for the blood sample taken one month post-vaccination, and who were not administered a vaccine not foreseen by the study protocol from 30 days before the booster administration until the post-vaccination blood sample, and who have not received a monovalent MenC conjugate vaccine or MenACWY conjugate vaccine because of suboptimal response to *N. meningitidis* serogroup C between the vaccination in the primary study MenACWY-TT-027 (108568) and the booster vaccine in this study. The interval between Visit 5 and Visit 6 for inclusion in the Booster ATP cohort for immunogenicity will be defined as 21 to 48 days.

10.4.2.4. Booster According To Protocol (ATP) cohort for immunogenicity – MenAWY

At post booster time point, the analysis of immunogenicity for MenA, W-135 and Y antibody titres will be done on Booster ATP cohort for immunogenicity – MenAWY. The Booster ATP cohort for immunogenicity – MenAWY cohort will include all evaluable subjects (i.e. those meeting all eligibility criteria, complying with the procedures defined in the protocol and with no elimination criteria during the study) from the Booster ATP cohort for safety for whom assay results are available for antibodies against at least one of the three antigens (MenA or MenW-135 or MenY) for the blood sample taken one month post-vaccination, and who were not administered a vaccine not foreseen by the study protocol from 30 days before the booster administration until the post-vaccination blood sample and who have not received a MenACWY conjugate vaccine because of sub-optimal response between the vaccination in the primary study MenACWY-TT-027 (108568) and the booster vaccine in this study. If a subject previously received monovalent MenC conjugate vaccine because of suboptimal response to *N. meningitidis* serogroup C after vaccination in the primary study MenACWY-TT-027 (108568), the subject

can still be included in the Booster ATP cohort for MenAWY. The interval between Visit 5 and Visit 6 for inclusion in the Booster ATP cohort for immunogenicity – MenAWY will be defined as 21 to 48 days.

10.5. Derived and transformed data

- For a given subject and a given immunogenicity measurement, missing or non-evaluable measurements will not be replaced. Therefore, an analysis will exclude subjects with missing or non-evaluable measurements.
- The cut-off value is defined by the laboratory before the analysis and is described in Section 5.7.3.
- A seronegative subject is a subject whose titre is below the cut-off value.
- A seropositive subject is a subject whose titre is greater than or equal to the cut-off value.
- The Geometric Mean Titres (GMTs) calculations are performed by taking the anti-log of the mean of the log titre transformations. Antibody titres below the cut-off value of the assay will be given an arbitrary value of half the cut-off value for the purpose of GMT calculation.
- rSBA booster response for serogroups A, C, W-135 and Y after the vaccine dose is defined as:
 - For initially seronegative subjects (pre-vaccination titer below the cut-off of 1:8): rSBA antibody titers ≥ 1:32 one month after vaccination, and
 - For initially seropositive subjects (pre-vaccination titer ≥ 1:8): rSBA antibody titers at least four times the pre-vaccination antibody titers, one month after vaccination.
- hSBA booster response for serogroups A, C, W-135 and Y after the vaccine dose is defined as:
 - For initially seronegative subjects (pre-vaccination hSBA titre below 1:4): hSBA antibody titres ≥1:8 one month after vaccination, and
 - For initially seropositive subjects (hSBA titer ≥1:4): a 4-fold increase in hSBA titres one month after vaccination.

10.5.1. Persistence analyses

10.5.1.1. Analysis of demographics/baseline characteristics

Demographic characteristics of each study cohort will be tabulated: age (in years) at Month X and months since the primary vaccination at persistence time point, gender, and geographic ancestry.

The mean age [in years] (at the persistence time point [with the range and standard deviation]) as well as the proportion of males and females will be calculated and presented by group.

The distribution of subjects enrolled at Month X among the study sites will be tabulated as a whole and per group and reason for not attending a visit at Month X among all subjects who participated in the primary vaccination study MenACWY-TT-027 (108658) will be summarized.

10.5.1.2. Analysis of persistence

For each Month X: The analysis of antibody persistence for MenC will be based on the ATP cohort for persistence – MenC – adapted for each time point. The analysis of antibody persistence for MenA, MenW-135 and MenY will be based on the ATP cohort for persistence – MenAWY – adapted for each time point. If, for any vaccine group, the percentage of subjects who come back for the Month X follow-up with serological results excluded from the ATP cohort is higher than 10%, a second analysis based on the Total Vaccinated Cohort Month X will be performed to complement the ATP analysis.

